- v. Once consented in-person or during the CS/EN call, maternal height and weight will be measured or self-reported by the participant to ensure participants fall within the BMI eligibility range (see inclusion/exclusion criteria).
- vi. They will then complete questionnaires (assessing sociodemographics, medication intake, psychosocial factors, health insurance, income, hospital and outpatient visits, quality of life, and executive functioning) read out-loud by Temple study staff to minimize literacy demands. Additionally, research staff will administer the ASA24 dietary recall during the combined CORE Screening/Enrollment visit or call (a tool that assesses participant dietary intake over the previous 24 hours).

- vii. Participants will then be enrolled and randomized 1:1 per computer-generated assignments in REDCap to healthy lifestyle intervention (A0; n=219) or usual WIC care (SC; n=219). Randomization will be stratified on weight status (overweight vs. obesity) and ethnicity (African American vs. Latina). [name] and her staff will be blinded to group assignment until participants reach randomization. Participants who choose not to participate, or who are ineligible, will be referred back to their WIC providers/Obstetricians for health/nutrition information.
- viii. If a call is needed/requested (e.g. due to Covid-19 restrictions on in-person visits), upon completion of the combined CS/EN call, participants will be sent via UPS a BodyTrace scale to use for weight at each time point. Additionally, they will be sent paper copies of their signed Informed Consent Form, the HIPAA Authorization, and the Medical Record Release forms (prenatal, delivery, infant, and WIC)

d. Inclusion and Exclusion Criteria

- i. Inclusion Criteria: All participants must meet all of the following criteria at screening
 1. Women at least 18 years of age
 2. Measured BMI between ≥ 25 kg/m²
 3. Self-identify as African American or Latina
 4. Philadelphia WIC participant
 5. Gestational age ≤ 16 weeks' by last menstrual period
 6. Willingness to receive study texts
 7. Own a cell phone with an unlimited text messaging plan
 8. Able to participate in light to moderate physical activity (walking)
 9. Participants must be willing to comply with all study-related procedures
 10. Participants must be able to read and write fluently in English or Spanish
- ii. Exclusion Criteria: If participants meet one of the following criteria, they will be excluded.
 1. Prior bariatric surgery

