- i. **Primary outcome.** *The primary outcome is the proportion of women with excessive gestational weight gain*, defined as the proportion of mothers exceeding weekly Institute of Medicine (IOM) weight gain targets (>0.32 kg/week for BMI 25-29.9 kg/m²; >0.27 kg/week for BMI ≥ 30 kg/m²) over the study period (from enrollment to end of pregnancy).⁵⁷ Total gestational weight gain will be calculated as the difference between weight in kilograms measured at 36-38 weeks' gestation (end of pregnancy) and weight at the baseline visit (in the first trimester or early second trimester of pregnancy). Weight in clinical gowns, without shoes, will be recorded in duplicate by trained staff using high-quality, calibrated SECA digital scales. We will also use BodyTrace scales for patients seeking a remote option (and/or during restrictions to in-person visits during the Covid-19 pandemic) that will be sent to the participant after completion of the combined CS/EN call. In the rare case that a mother delivers her infant before 36-38 weeks' gestation, we will abstract her last prenatal weight from her obstetric chart and call her within 2 weeks of delivery to administer our follow-up

survey. We expect to abstract weights in <10% of mothers based on previous experiences with the target population. Height will be measured to the nearest 0.1 cm using a calibrated stadiometer at participants' in-person baseline assessments or via self-report via phone.

ii. **Secondary and patient-centered outcomes.**

1. ***Dietary intake*** will be measured using the Automated Self-Administered 24-hour (ASA24) dietary assessment tool, a web application developed by NCI.⁶⁹ We will collect one 24-hour dietary recall during combined CS/EN visit or call and during the end of pregnancy visit. Data are summarized as intake of micro- and macronutrients, food groups, and dietary patterns. ASA24 has been validated against more expensive, time-consuming tools.⁷¹ We have experience using this measure in diverse groups.^{48,49}

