1. **Primary aim.** We will use Fisher's exact test (for raw intervention effects) as well as multivariable logistic regression (for adjusted intervention effects), testing the effect of treatment group on the odds of excessive gestational weight gain while simultaneously adjusting for covariates discovered to be unbalanced between the trial arms at baseline. We will consider interaction effects of treatment by relevant baseline predictors when needed, (e.g., age, parity, BMI, and gestational age at enrollment), to evaluate the assumption of equal intervention effects between the 2 arms with respect to these covariates. Data will be analyzed using an intention-to-treat (ITT) approach where subjects are analyzed according to their treatment assignment at randomization, regardless of level of engagement. Since an ITT analysis is planned, 2 methods are proposed for accounting for missing data. First, multiple imputation methods will be used to estimate weight at 36-38 weeks' gestation based on intermediate outcomes, mediating variables, and data collected on subjects with complete follow-up.^{87,88} A second approach will utilize model-based analyses with direct maximum likelihood methods.⁸⁹

Additionally, to take advantage of the longitudinal nature of this study, we will treat weight as a continuous measure, employing an advanced mixed-effects modeling approach to estimate individual and mean weight trajectories over time by treatment group. We will supplement weights collected by research staff with available electronic health record prenatal weight data abstracted from WIC and/or participants' obstetric records; we and others have found that the absolute agreement between research and prenatal clinic measured weights is extremely high, providing strong support for exchangeability.^{90,91} Benefits of this modeling approach include: 1) ability to accommodate all available measured prenatal weight data; 2) allowance for varying and/or unequally-spaced intervals between measurements; and 3) high variability in the number of longitudinal assessments expected across subjects. Longitudinal trajectories could be modeled using splines or kernel density.⁹² They will allow for an unbiased estimation of the overall intervention effect on gestational weight gain to better understand non-linear, dynamic changes in weight over time.

2. **Additional aims.** We will use parallel strategies to those described above for secondary and patient-centered outcomes.

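### The adjusted primary model picks its covariates by chance baseline imbalance and does not fix the stratification factors; the plan also does not say whether it or Fisher's test decides

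*Combined protocol and SAP*

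**What the plan says.** Section 8.c.vii: "Randomization will be stratified on weight status (overweight vs. obesity) and ethnicity (African American vs. Latina"). No block scheme is described.

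Section 9.d.i defines the outcome as "the proportion of mothers exceeding weekly Institute of Medicine (IOM) weight gain targets (>0.32 kg/week for BMI 25-29.9" kg/m², with a cut-off of 0.27 kg/week at BMI 30 or above. The weight-status stratum therefore decides which threshold a woman is judged by.

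Section 9.d.iii.1 gives two analyses of this outcome, Fisher's "exact test (for raw intervention effects) as well as multivariable logistic regression (for adjusted intervention effects"). They are listed side by side without a ranking. The regression works by "simultaneously adjusting for covariates discovered to be unbalanced between the trial arms at baseline". No candidate list or measure of imbalance is given. The plan does name "relevant baseline predictors when needed, (e.g., age, parity, BMI, and gestational age at enrollment"), but only for optional treatment interactions. Ethnicity does not appear in the primary-analysis text.

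For missing outcomes, "multiple imputation methods will be used to estimate weight at 36-38" weeks, and then "A second approach will utilize model-based analyses with direct maximum likelihood methods". Neither is called primary.

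Section 9.d.iii.2 extends the approach: "We will use parallel strategies to those described above for secondary and patient-centered outcomes". Section 9.d.iii.4 bases the sample size on a difference in proportions and names no test.

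**The concern.** Under randomisation a baseline imbalance is a chance event. A rule that adjusts only where imbalance appears can admit variables unrelated to weight gain and omit those that predict it. It also gives no assured place to the stratification factors, which are the covariates with the clearest claim to be in the model.

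The covariate set is settled only once the baseline table is seen. Two competent analysts could follow the section, fit different models and both comply. If the adjusted model and Fisher's test then fell on opposite sides of 0.05, no written rule would say which result stands. At stake is whether the adjusted odds ratio can be reproduced, and a little power. The validity of the sample size is not at stake.

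**Working it through.** **1. The plan's own figures.** Inputs from section 9.d.iii.4: 40% vs 55%, two-sided alpha 0.05, power 0.80, 15% loss.

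- Uncorrected: n₀ = [1.960·√(2·0.475·0.525) + 0.8416·√(0.40·0.60 + 0.55·0.45)]² / 0.15² = 172.8, so 173 per arm.
- Continuity-corrected: (n₀/4)·[1 + √(1 + 4/(n₀·0.15))]² = 185.9, so 186 per arm, as stated.
- Loss: 186/0.85 = 218.8, so 219 per arm and 438 in total, as stated.
- Exact Fisher power at 186 per arm, by enumeration: 0.811 (40% vs 55%) and 0.969 (40% vs 60%). Both meet the stated 0.80 and 0.96. Its exact size is 0.039 to 0.043 at common rates of 40% to 55%.

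**2. Link between weight status and outcome.** Assume normal weekly gain with equal means in both BMI classes and an overall rate of 47.5%. The 0.05 kg/week gap between cut-offs alone then gives these odds ratios (obesity vs overweight):

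| Assumed SD, kg/week | 0.15 | 0.20 | 0.25 | 0.30 |
|---|---|---|---|---|
| OR | 1.70 | 1.49 | 1.38 | 1.31 |

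A true difference in gain between the classes could offset this.

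**3. What the rule selects.** With k independent candidates, the chance that at least one enters is 1 − (1 − q)^k. For a p<0.05 criterion q = 0.05. For a standardised difference above 0.1 at 219 per arm, z = 0.1/√(2/219) = 1.046, so q = 0.295. Both criteria and k are assumptions, since the plan gives none.

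| k | p<0.05 | standardised difference >0.1 |
|---|---|---|
| 5 | 23% | 83% |
| 10 | 40% | 97% |
| 20 | 64% | 99.9% |

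These figures show how far the covariate set depends on the analyst. They do not show that the treatment conclusion changes.

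**4. Type I error.** Simulated size of the imbalance-selected model alone is 0.039 to 0.050 (20,000 trials per scenario); a smaller run with other prognostic strengths gave 0.052 (4,000 trials, Monte Carlo SE about 0.004). If either Fisher's test or the selected model may be claimed, size is 0.047 to 0.055 across two sets of assumptions, and 0.055 to 0.067 if the imbalance cut-off is also free.

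**5. Power.** Set-up: 20,000 trials per scenario; 438 randomised; random loss to 372; marginal rates 55% and 40%; a 60/40 split in each stratification factor; eight further baseline variables, of which 0, 1 or 2 are prognostic at OR 1.6 per SD. The fixed set is the strata plus three covariates. All of these except N, the rates and the loss are assumptions.

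| Strata randomised | ORs: weight status, ethnicity | Prognostic covariates | Fixed set | Imbalance, p<0.05 | Imbalance, std. diff. >0.1 |
|---|---|---|---|---|---|
| Blocks of 4 | 1, 1 | 0 | 0.827 | 0.829 | 0.822 |
| Blocks of 4 | 1, 1 | 1 | 0.845 | 0.830 | 0.830 |
| Blocks of 4 | 2, 2 | 1 | 0.863 | 0.838 | 0.838 |
| Blocks of 4 | 3, 2 | 2 | 0.883 | 0.839 | 0.842 |
| No blocks | 1, 1 | 1 | 0.839 | 0.825 | 0.827 |
| No blocks | 2, 2 | 1 | 0.861 | 0.831 | 0.839 |
| No blocks | 3, 2 | 2 | 0.879 | 0.826 | 0.842 |

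The gain runs from about zero to 5.3 points (0.879 − 0.826). Under multiple imputation (4,000 trials per scenario) it was 2.0 to 4.7 points in the scenarios with prognostic strata and covariates. Adjusting for the strata alone, with blocks, moved power from 0.835 to 0.834 when only weight status mattered at OR 1.5, and from 0.842 to 0.862 at ORs of 3 and 2. At the size of effect in step 2, then, weight status alone buys almost nothing.

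**The case against.** **Fisher's test already leads.** It is listed first, the hypothesis is framed as prevalence, and 186 is the continuity-corrected size, which approximates Fisher's test. This is a fair inference, but no sentence says so, and the adjusted estimate would still rest on the imbalance rule. It does stand that making a logistic model primary is a preference, not a correction: one sentence naming Fisher's test would settle which analysis decides.

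**The rule may not exclude the stratification factors.** This stands. With permuted blocks a factor entered in 0 of 20,000 trials per scenario. Without blocks one entered in about 10% (p<0.05) or 50% (standardised difference >0.1). The plan states no blocking, so what can be said is that the factors are not fixed in the model, not that they will be left out.

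**Little harm is shown.** This largely stands. A reader might infer that disagreement between Fisher's test and the adjusted model measures the damage from covariate selection. It does not. At 186 per arm and 55% vs 40%, Fisher's test and a Wald test with no covariates already disagree in 2.7% of trials (power 0.838 − 0.811 = 0.027), simply because Fisher's test is conservative.

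**The missing-data methods are ordered.** The words first and second could be read as a ranking. This is a separate wording point and does not carry the concern.

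**Conclusion.** The concern holds as a prespecification weakness with a better method available at no cost. The stated rule selects on chance imbalance, does not fix the stratification factors in the model, and sits beside Fisher's test with no statement of which decides.

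Three stronger readings are not supported. The sample size and power are not wrong; they reproduce. The imbalance rule does not by itself materially inflate type I error, and free choice between analyses does so only modestly, on assumed prognostic strengths. Nor do the documents show that weight status is prognostic: the OR of 1.3 to 1.7 needs equal mean gain in both classes and an assumed SD.

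The sure gain from a change is a reproducible adjusted estimate at the same N. The possible gain is about 0 to 5 points of power, and none if the covariates are not prognostic. The strata mix, odds ratios, number of candidates, blocking and SD are all assumptions. This should be fixed, but it does not threaten the trial.

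**What to change.** Before any arm-level outcome data are seen, amend section 9.d.iii.1 as follows.

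- Delete the imbalance rule. Fix the adjusted model as arm, weight status, ethnicity, gestational age at enrolment, age and parity; continuous BMI may be added, since the plan names it as a predictor and a two-level split discards variation within classes.
- Name the primary analysis. Preferably this is the fixed model, reported as an odds ratio with a standardised risk difference, with Fisher's test as unadjusted support. At minimum, name Fisher's test as primary and keep the fixed model as the prespecified adjusted estimate.
- As a secondary wording point, say which missing-data method is primary. If it is multiple imputation, pool the model estimate over the imputations.
- In section 9.d.iii.2, use the same fixed set for secondary outcomes, plus the baseline value where one is measured, such as the ASA24 recall.

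The cost is wording only. The covariates are already collected at screening or the CS/EN assessment, and N stays at 438. The timing condition needs confirming: this version was approved in September 2021, completion was planned for December 2023, staff blinding is described only up to randomisation (section 8.c.vii), and WIC nutritionists can view intervention weights (section 9.c.iii.2). If arm-level outcomes have already been seen, report the change as made afterwards.

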Once a participant enters her data, she will **receive immediate personalized self-monitoring feedback** through text messaging to reinforce successes and/or offer motivational strategies (see example from Healthy Babies). We will additionally send intervention participants **text message prompts to self-weigh weekly using study provided scales from BodyTrace**. These scales transmit weight data directly through the cellular network. Progress will be displayed via links to web-based graphs that participants (and WIC nutritionists) can easily access to visualize gestational weight gains. We have used BodyTrace scales in several studies with >90% compliance for self-weighing.^{28,48,49}

3. Tailored skills training materials: Tailored materials can enhance the personal relevancy of interventions, provide cues to action, and increase engagement.⁵⁰ We will offer intervention participants' skills training content that corresponds to their assigned behavior change goals via videos and text messages sent 3 times weekly (frequency of texts was determined with input from Healthy Babies participants and review of mHealth literature, suggesting that informational texts should not be delivered daily).⁵¹⁻⁵³ We have a library of materials that have been adapted for this study, with topics including (but not limited to): negotiating barriers; stress reduction; eating out; serving sizes; and engaging social support – all designed for mothers

from resource constrained settings with low-literacy levels (example skills text: “Craving something sweet? Instead of grabbing junk, eat applesauce, yogurt, or a fruit cup. Ur baby will thank u ☺”). We created ~1 minute videos including messages from WIC nutritionists and narratives from previous study participants, providing role models with information about cost and community resources to increase receptivity. All materials will be available in English and Spanish, with specific content tailored to ethnicity (either African American or Latina), to offer relevancy to all participants enrolled.

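### Does leaving the imputation inputs unlisted for a missed 36-38-week weight put the primary comparison at risk?

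*Combined protocol and SAP*

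**What the plan says.** Section 9.d.i (Primary outcome) takes the 36-38-week weight minus the baseline weight and compares weekly gain with 0.32 or 0.27 kg/week, depending on BMI. It names a chart weight for one situation: "In the rare case that a mother delivers her infant before 36-38 weeks" of gestation, her last prenatal chart weight is used. It adds: "We expect to abstract weights in <10% of mothers based on previous experiences with the target population".

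Section 9.d.iii.1 (Primary aim) covers other missing end weights within an intention-to-treat analysis. First, "multiple imputation methods will be used to estimate weight at 36-38 weeks" of gestation, "based on intermediate outcomes, mediating variables, and data collected on subjects with complete follow-up". Then: "A second approach will utilize model-based analyses with direct maximum likelihood methods". Neither sentence lists weight sources, and neither method is marked as leading.

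The next paragraph, on the continuous mixed-effects model, adds prenatal weights from WIC and obstetric records to the study weights, on the ground that "the absolute agreement between research and prenatal clinic measured weights is extremely high". Section 9.b and its record-review items collect those weights without distinction by arm.

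Section 9.c.iii.2 sends intervention participants "text message prompts to self-weigh weekly using study provided scales from BodyTrace". Section 14 gives a scale to every enrolled woman, for use at study time points.

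**The concern.** A woman who is still pregnant but misses the 36-38-week weighing may have a clinic weight on file from about the same date. The primary-outcome text does not call on it, and the missing-data text does not name it as an input. Meanwhile the undefined reference to intermediate outcomes could be stretched to cover home-scale readings, which are prompted in one arm only.

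If gain itself influences who misses the visit, interim weights help to recover the missing outcomes. Using them in one arm alone would correct that arm and leave the other uncorrected, which could bias the primary risk difference. Two analysts could also read the same sentence and choose different inputs.

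**Working it through.** **1. The plan's own figure.** Inputs from Section 9.d.iii.4: 40% vs 55%, two-sided alpha 0.05, power 0.80, 15% loss.

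- Mean proportion 0.475. n = [1.960 × √(2 × 0.475 × 0.525) + 0.842 × √(0.40 × 0.60 + 0.55 × 0.45)]² / 0.15² = 172.8, so 173 per arm without continuity correction.
- With continuity correction: (172.8/4) × [1 + √(1 + 4/(172.8 × 0.15))]² = 185.9, so 186.
- Inflation: 186/0.85 = 218.8, so 219 per arm and 438 in total.

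The stated figures reproduce. Exact Fisher power at 186 per arm is 0.811 (40% vs 55%) and 0.969 (40% vs 60%). None of this depends on the imputation inputs.

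**2. How many women are at issue.** 219 − 186 = 33 per arm (15.1%). The allowance pools miscarriage with loss to follow-up, so 33 is an upper limit for continuing pregnancies with a missed weight. The documents give no split.

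**3. What the imputation sentence can refer to.** Table 1 has no study time point between baseline and 36 weeks. The interim data that the plan collects for everyone come from charts and WIC records: prenatal weights and the 24-28-week glucose results. Mediators, where Section 9.d.iii.2 names them, are diet and physical activity changes, not home weights. When Section 9.d.iii.1 names supplementary weight sources in its next paragraph, it names WIC and obstetric records and not the home scale. Section 9.c.iii.2 presents weekly readings as self-monitoring with progress graphs. The natural reading is therefore interim clinic weights from both arms.

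**4. Size of the asymmetry if home readings were used.** Latest entry (16 weeks) to earliest end visit (36 weeks): 36 − 16 = 20 prompts. At the 90% compliance level that the plan cites, 0.9 × 20 = 18 readings, against none prompted in usual care. Women who miss the end visit would probably send fewer.

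**5. What the asymmetry could do.** Illustrative simulation; the assumptions are not document figures. 15% are missing, the odds of missingness multiply by 1.5 to 3 per SD of gain, interim and final gain correlate at 0.9, and imputation is done within arm. Risk difference (intervention minus usual care), in percentage points:

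| True difference | Odds ratio | Interim weights in neither arm | Intervention arm only | Both arms |
|---|---|---|---|---|
| 0 | 1.5 | +0.1 | +1.8 | 0.0 |
| 0 | 2 | 0.0 | +3.1 | −0.1 |
| 0 | 3 | 0.0 | +4.4 | 0.0 |
| −15 | 1.5 | −14.9 | −13.2 | −15.0 |
| −15 | 2 | −15.2 | −12.1 | −15.1 |
| −15 | 3 | −15.6 | −10.8 | −15.3 |

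With the same inputs in both arms the error is at most 0.3 point. The 1.8 to 4.4 point shift appears only in the one-arm column, and its sign reverses if low gainers are the ones missing.

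**6. Outer bounds.** With 40% and 55% observed in 186 per arm: (186/219) × (−15) ± (33/219) × 100 = −12.7 ± 15.1, that is −27.8 to +2.3 points. Any binary outcome with this much missing data has bounds this wide, so they say nothing specific about the choice of inputs.

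**The case for a change.** The strongest case for a change is that the text permits the bad reading, that one sentence would exclude it, and that the better data are already being collected. The plan calls clinic and research weights exchangeable yet commits the clinic weights only to the continuous model. Maximum likelihood may not help either: for a single binary outcome with fully observed baseline covariates it reduces to complete cases unless interim weights are modelled jointly.

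Part of this stands. The predictor list is unstated and no lead method is named. But this is silence, not a prohibition or a contradiction. The complete-case argument tests a logistic model that the plan does not specify. The plan's wording is equally open to a joint model of the weights, and the mixed model described next uses all available prenatal weights from both arms. Nor are women with missing weights dropped, since the intention-to-treat analysis imputes them.

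The firmer remedy would make a near-window clinic weight the primary value and bar unscheduled home readings. That is a trade-off, not a clear gain. At in-person visits, "Weight in clinical gowns, without shoes, will be recorded in duplicate by trained staff"; a clinic weight taken under other conditions would be treated as exact next to a cut-off, whereas imputation carries its uncertainty. Any window width, such as two weeks, is arbitrary. BodyTrace is also the study's own remote instrument in both arms, so barring its readings would need a rule to separate a study weight from a home weight taken in the same weeks. Reasonable statisticians would differ on this.

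**Conclusion.** No change is needed. The plan leaves the imputation inputs to the analyst, and the data it collects point to a sound choice: dated chart and WIC weights, the same in both arms. The mixed model on all prenatal weights gives a cross-check from both arms.

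No effect on sample size or power arises, and no effect on the risk difference can be derived from the documents. The 1.8 to 4.4 point shift needs three things together: missingness that depends on gain beyond what the shared data explain, home readings used as inputs, and no comparable weights used in usual care. The plan states none of these.

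The conclusion assumes that chart and WIC abstraction is about equally complete in the two arms and that the analyst uses the same sources in each.
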